
Justification

We wish to demonstrate that the use of with autologous MSCs is effective as a treatment option for knee OA grades, II and III. In a large number of cases it is possible to improve the pain, function and quality of life of patients without the side effects of conventional treatments. In other cases, avoid progression to more severe stages that require joint replacement surgery. This research aims at contributing with a low-cost regenerative technique in order to change the course of the disease and significantly reduce public and private sector expenses generated by conservative and surgical OA treatments.

Main goals

- a. The aim of the present study will be to compare three types of intra-articular injections of MSC populations obtained from two clinically relevant sources: injections containing BM-MSC or AD-MSC or a combination of both of them BM-MSC and AD-MSC, in a randomized non blind clinical trial.
- b. To assess the efficacy and safety of treatment with containing BM-MSC or AD-MSC or a combination of both of them BM-MSC and AD-MSC, in relation to pain, function and quality of life in patients with knee OA.

Hypothesis Testing

H1: The combined use of BM-MSC and AD-MSC is superior for pain management in knee OA, than the use of BMSC or AD-MSC alone.

H0: The combined use of MSC from bone marrow and adipose tissue is not superior to the use of MSC derived solely from bone marrow or solely from adipose tissue in the treatment of pain and function in patients with knee OA.

MATERIALS AND METHODS

1. Study design

The present study will be conducted from June 2020 to December 2021 at the Omnihospital, an affiliated center to the Universidad Católica de Santiago de Guayaquil Ecuador, and the support of the Instituto de Investigación e Innovación de Salud Integral, Medical Faculty of the same University and Maastricht University, The Netherlands. This will be a phase III trial, triple arm randomized open label dose to be conducted as a single intra-articular injection of MSC in 3 groups of patients with the diagnosis of knee OA grade II and III (Ahlbäck classification),²² one receiving BM-MSC other receiving AD-MSC and the other BM-MSC + AD-MSC.

2. Study population

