- i. Pain, function and quality of life will be assessed using VAS and WOMAC scales. All patients will be evaluated before treatment, and at 1, 3, 6, 9 and 12 months.
- ii. Magnetic resonance with T2 Map imaging will be performed at baseline to analyze cartilage damage and at 6 months control. This test allows the early diagnosis of areas of cartilage degeneration. In addition it evaluates the relaxation times of water, collagen and proteoglycans. Sequence to assess the structure of the cartilage²⁵.

5. Randomization.

A randomized non blind clinical trial with active control. For this purpose, the random number generator, found on the RANDOM.ORG ® website (available at <https://www.random.org/integers/>)²⁶ will be used to generate 31 random numbers. Value between 0 and 1. Format: 5 columns.

[figure not shown]

Figure 1: Study Design. W (week), M (month), V (visit), VAS (visual analogue scale), WOMAC (Western Ontario Mc Master University Osteoarthritis Index)

6. Procedures

a. **Stem cell obtaining procedures.**

All the procedures will be performed in the operating rooms of the Omnihospital by [name] and [name], both certified orthopedic surgeons. Both will know about the randomization in order to know the source from which MSCs will be obtained, in an ambulatory procedure under local anesthesia and sedation. Average procedure time to obtain de MSCs will be approximately 75 minutes.

b. **BM-MSc PROCEDURE. GROUP 1**

- i. Bone marrow aspiration will be performed using a standard surgical technique: fluoroscopically guided percutaneous puncture of posterior iliac crest bone.
- ii. A total of 60 ml of blood from bone marrow will be aspirated with a heparinized syringe.
- iii. Attach the heparinized syringe to a 150 um filter. Gentle push the bone marrow through the filter to another syringe.
- iv. Attach 45 degree dispensing tip to filtered bone marrow 60 cc syringe.
- v. Slowly transfer the BMA into the Neogenesis 60 cc kit concentrating device until you have reached the 60 cc mark. Secure the green cap and clear safety cap.
- vi. Centrifugation of Neogenesis 60 cc concentrating device. Match counterbalance for each concentrating devices +/- 1.0g. Spin at 4200 rpm / 2800 rcf for 10 minutes.
- vii. Place the concentrating device on the BPS (Benchtop processing station), secure the device with your right hand and slowly turn the knob with your left hand counterclockwise, until the bone marrow aspirate has reached the bottom of the luer slip fitting.

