- viii. Place the "waste 60cc syringe" vertically on the Neogenesis 60 cc concentrating device. Using the BPS, push the PPP into the 60cc syringe until the buffy coat reaches 20ml outlined on the concentration device.
- ix. Remove the "60cc waste syringe". Place the "60cc Bone marrow collection" syringe on the concentrating device.
- x. Using the BPS push the remaining bone marrow until the syringe captures the buffy coat, a total volume of 10 - 20 cc. Cap the bone marrow collection syringe.
- xi. One ml of the total bone marrow will be sent for flow cytometry testing.
- xii. Subsequently, a single percutaneous intra-articular injection of the obtained MSCs will be done into the affected knee.

c. **AD-MSC PROCEDURE. GROUP 2.**

- i. Local anesthesia with Klein tumescent solution will be applied in the region of greater trochanter of hip and gluteus.
- ii. A 40 ml of pure fat will be extracted with two 60 ml syringe and 2.5 to 3 mm diameter cannula with equal luer lock spike. Physiological solution will be added and subsequently decanted in order to discard infranatant and remove traces of tumescence and blood (Repeat 2-3 times).
- iii. The obtained adipose tissue will be introduced into two 50 ml conical tubes. Reconstituted collagenase will be added with a 0.22 micron filter, 15 ml to each tube.
- iv. The tubes will be shaken for 20 minutes by placing them in the heater block or shaker. Then the two tubes will be centrifuged at 900 g for 5 minutes.
- v. Adipose tissue and saline supernatant will be carefully removed until the remaining pellet be approximately 5 ml. Using a pipette connected to the 20 ml syringe the pellet of stromal vascular factor will be extracted.
- vi. The obtained pellet will be transferred into two new sterile 50 ml tubes. Saline solution will be added until 45 ml be completed.
- vii. The cells of conical bottom of each of the tubes will be aspirated with a 20 ml syringe and pipette. A total volume of about 5 ml will be obtained.
- viii. In a new sterile 50 ml tube we will place a 100 µm cell strainer in order to gently transfer the cell suspension. Stromal vascular fraction (SVF) will be aspirated.
- ix. A 1 cc of the adipose tissue stem cell concentrate will be sent to the Molecular Biology Laboratory for quantification by flow cytometry in order to determine the volume and viability of obtained stem cells.

d. **BM-MSC + AD-MSC PROCEDURE. GROUP 3.**

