- i. AD-MSC will be joined with BM-MSC in a same syringe for application of the percutaneous injection (AD MSC + BM MSC group) into the affected knee.

7. FOLLOW UP.

All patients will be evaluated measuring scores of the WOMAC (Western Ontario and McMaster Universities Osteoarthritis Index)²³ and the VAS (Visual Analogue Scale), before treatment and then at 1, 3, 6, 9 and 12 months.

STUDY FLOW CHART
MSC IN OA

Patient: _____

STUDY FLOW CHART	VISIT 1	VISIT 2	VISIT 3	VISIT 4	VISIT 5	VISIT 6	VISIT 7	VISIT 8	VISIT 9	VISIT 10
Protocol Concept Sheet	Week 1	Week 2	Week 3	Week 4	Week 6	Month 3	Month 6	Month 9	Month 12	Month 15
Diagnosis	X	X								
Orthopaedic exam	X									
X RAYS		X								
MRI T2 map		X								
Laboratory		X								
Inclusion/Exclusion		X								
Informed Consent		X								
Pre Op Evaluations		X								
VAS		X								
WOMAC		X								
Preparation	X		X							
Randomization				X						
Procedures					X					
BM MSC					X					
AD MSC					X					
Flow Citometry Order					X					
Post Op Evaluations					X					
Sticks removed					X					
VAS						X	X	X	X	
WOMAC						X	X	X	X	
MRI T2 map							X			
Adverse Event Evaluation					X	X	X	X	X	
Results										X

MD. Signature

Date.

[figure not shown]
Figure 2. Clinical Trial MSC/OA Protocol Sheet.

Statistical Analysis.

The sample size is determined using the tool of G*Power VERSION 3.0.10. The parameters are applied for the selected F test, two-way mixed ANOVA (repeated measures, with immediate interaction). Given that none of these approaches have been previously compared, either separately or combined, the calculation was conducted considering a medium effect size ($f=0.25$). We established an error probability α of 0.05 and power of 0.95. We calculated the application of 3 repeated measures, even though 6 measures will be conducted for some variables (i.e., the VAS or WOMAC questionnaire).

Based on this criteria, the sample size would be 54, meaning that each group will consist of 18 individuals. The information previously mentioned is represented in detail in the following table and illustrated in a graph below it.

F tests - ANOVA: Repeated measures, within-between interaction		
Analysis:	A priori: Compute required sample size	
Input:	Effect size f	= 0.25
	α err prob	= 0.05
	Power (1- β err prob)	= 0.95
	Number of groups	= 3
	Repetitions	= 3
	Corr among rep measures	= 0.5
	Nonsphericity correction ϵ	= 1
Output:	Noncentrality parameter λ	= 20.250000

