This study applies descriptive statistics for determining the frequency and proportions for demographic variables (age, gender, education, and ethnicity) and clinical states (severity of knee osteoarthritis, time with disease, comorbidities). Likewise, for calculating the mean and standard deviation of age, WOMAC scores (and each element of the scale) and VAS.

We utilize the two-way mixed ANOVA to compare the differences of means between treatment groups for each dependent variable (WOMAC scores, VAS, and radiological changes). With respect to the WOMAC scores, not only we will analyze the scores in general, but also each score value of the three different components separately (pain, stiffness, function). The tests will determine if there is an interaction between the dependent variable and the factors (independent variables). The factors will be the type of treatment (between subjects) and time (within subjects). For the type of treatment, it

is categorized into: BMSCS only, AD-MSc only, and BM-MSc and AD-MSc combined.

As for the time factor, this will differ according to the dependent variable held for analysis. For example, the analysis of WOMAC and EAV scores will be evaluated in 6 different periods of time. The patients will be asked to respond to our questionnaires three weeks before the intervention and 1, 3, 6, 9, and 12 months after intervention (surgery). With respect to radiological changes, the T2 mapping MRI will be performed twice before the procedure and again six months later.

To guarantee the reliability of the analysis, we will test the atypical values by utilizing box diagrams and the normality with the method of Shapiro-Wilk. Furthermore, the homogeneity of variations will be evaluated with inferential statistic Levene tests, while the homogeneity of covariances with multivariate statistical Box's M test. Consequently, to comply with the hypothesis sphericity, a Mauchly's test will be conducted. In the case of a violation of an assumption, different tests will be utilized.

Finally, in the case of a treatment complication, there will be mixed lineal models generalized for determining the probability of each intervention. The complications considered in this investigation are pain and hematomas in the surgical place where stem cells were extracted, knee pain, and synovial effusion.

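### Randomisation sits at a separate visit before the procedure, so open-label loss before treatment could differ by arm, and no rule covers patients randomised but not treated

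*Combined protocol and SAP*

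**What the plan says.** **Timing.** In the Study Flow Chart (section 7), the mark "Randomization X" falls under Visit 4, Week 4, and nothing else is marked there. The procedure rows, including both cell sources and flow cytometry, fall under Visit 5, Week 6. Inclusion/exclusion and consent are marked at Visit 2, Week 2. Eligibility is not marked again.

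**Blinding.** Section 1 describes the trial as "triple arm randomized open label dose to be conducted as a single intra-articular injection of MSC". Of the two operating surgeons, section 6.a says "Both will know about the randomization in order to know the source from which MSCs will be obtained". No section says when patients learn their arm.

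**Harvest.** Group 1 has "fluoroscopically guided percutaneous puncture of posterior iliac crest bone" (section 6.b). In Group 2, "A 40 ml of pure fat will be extracted with two 60 ml syringe" (section 6.c). For Group 3, "AD-MSC will be joined with BM-MSC in a same syringe for application of the percutaneous injection" (section 6.d), so both harvests are needed.

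**Outcome timing.** The Statistical Analysis section times the post-baseline questionnaires at "1, 3, 6, 9, and 12 months after intervention (surgery". Sections 4.c and 7 say that all patients will be assessed at those months. The chart shows post-operative VAS and WOMAC at Months 3, 6, 9 and 12, without stating the origin of the count.

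**Analysis.** The plan is a two-way mixed ANOVA in SPSS. It names no analysis set, no rule for patients randomised but untreated, no replacement rule and no missing-data method. The calculated sample size of 54 is also the number to be recruited.

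**The concern.** Randomisation protects the comparison only if the patients analysed are those who were randomised. Here the allocation exists for some time before anyone is treated, in a trial where nothing conceals it and the arms ask different things of the patient. A patient may decline two harvests after having been willing to have one. A surgeon may defer a patient for a reason that carries weight for one arm only. An exclusion such as active infection may also arise after Week 2.

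If these patients have no post-baseline scores, a conventional mixed ANOVA omits them, and the groups compared are no longer the randomised groups. H1 claims that the combination is superior to either source alone. Every comparison bearing on H1 therefore involves Group 3, the arm where refusal or deferral is most plausible, and the outcome is self-reported pain. Recruiting more patients would restore power but would not remove selection that differs by arm.

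**Working it through.** **1. Length of the interval.** The documents allow three readings.

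| Source | Anchor | Implied procedure week | Interval after Week 4 |
|---|---|---|---|
| Flow chart | Procedures under Visit 5 | 6 | 2 weeks |
| Statistical Analysis | Questionnaires three weeks before the intervention; chart has them at Week 2 | 2 + 3 = 5 | 1 week |
| Section 4.a.vii | Matrix preparation three weeks before, injections in weeks 1 and 3 | 1 + 3 = 4, or 3 + 3 = 6 | 0 or 2 weeks |

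Section 4.a.vii agrees with the chart if the three weeks are counted from the second injection, and not if counted from the first. The Week 6 column also holds post-operative evaluation and a removal step, so it may not be a single procedure day. Figure 1 is not available to settle this. The chart does, however, put randomisation and procedure at two separate visits.

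**2. The plan's own sample size.** Inputs from the G*Power table: f = 0.25, α = 0.05, k = 3 groups, m = 3 repetitions, ρ = 0.5, nonsphericity correction 1. The text states "We established an error probability α of 0.05 and power of 0.95".

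- λ = f²·N·m/(1 − ρ) = 0.0625 × 54 × 3/0.5 = 20.25, as printed in the plan.
- df1 = (k − 1)(m − 1) = 4; df2 = (N − k)(m − 1) = 51 × 2 = 102.
- Power from the noncentral F distribution = 0.958. The smallest N reaching 0.95 is 52, which rounds up to 54 for equal arms. The plan's figure reproduces.

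**3. Power if patients are lost before treatment and omitted.** The number lost is an assumption throughout, because the documents give none.

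Spread evenly (same formula, N reduced):

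| Lost | N | λ | Power |
|---|---|---|---|
| 0 | 54 | 20.25 | 0.958 |
| 2 | 52 | 19.50 | 0.950 |
| 3 | 51 | 19.125 | 0.946 |
| 5 | 49 | 18.375 | 0.936 |
| 8 | 46 | 17.25 | 0.918 |

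All lost from Group 3, assuming that Group 3 differs and Groups 1 and 2 are alike. Then λ = 20.25 × S/12, where S = Σ nᵢ(gᵢ − ḡ)² with g = (0, 0, 1), ḡ is the mean weighted by arm size, and S = 12 for arms of 18/18/18:

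| Arms | S | λ | Power |
|---|---|---|---|
| 18/18/17 | 11.55 | 19.49 | 0.950 |
| 18/18/16 | 11.08 | 18.69 | 0.941 |
| 18/18/14 | 10.08 | 17.01 | 0.915 |

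Power falls below 0.95 at the third loss if losses are spread evenly, and at the second if all fall in Group 3. The decline is modest in either case.

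**4. Selection.** Each loss is 1/18 = 5.6% of an arm. Suppose a fraction d of an arm is lost, and those patients' mean outcome would have differed by D from that of the patients kept. The mean of the kept patients then departs from the full-arm mean by d × D. With D assumed between 0.5 and 1 SD:

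- one lost: 0.056 × 0.5 to 0.056 × 1 = 0.03 to 0.06 SD;
- two lost: 0.111 × 0.5 to 0.111 × 1 = 0.06 to 0.11 SD;
- four lost: 0.222 × 0.5 to 0.222 × 1 = 0.11 to 0.22 SD.

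The shift cancels between arms only if loss is alike in all three.

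**5. Chance of any loss.** At an assumed 2% per patient, 1 − 0.98⁵⁴ = 0.66. At 5%, 1 − 0.95⁵⁴ = 0.94. Even a low rate makes it likely that the plan will need a rule it does not have.

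**The case against.** The case against is substantial, and several parts of it stand.

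- **Patients' knowledge.** A reader might infer that patients know for two weeks which harvest awaits them. The documents do not say so. Only the surgeons are expressly said to know, and even for them no date is given. Patient knowledge is a reasonable inference from an open-label design, but deferral by an informed surgeon would be enough to create the problem.
- **The two weeks.** That length rests on the chart and is in tension with other sections. It should be treated as unsettled.
- **Follow-up.** A reader might infer that untreated patients are barred from follow-up. They are not: sections 4.c and 7 speak of all patients. What is missing is a date origin for a patient who has no surgery, and a rule that keeps that patient in the analysis. Missing data over the following 12 months is a separate matter, which moving randomisation does not solve.
- **Direction and rate.** No withdrawal rate can be taken from the documents, for any arm. Some losses, such as an intercurrent infection, need not depend on the arm. Unequal arms are not a defect in themselves, since a mixed ANOVA accepts them.
- **Existing protection.** Consent precedes randomisation, and section 3 requires that patients be told of the study aims and of alternative treatments. This lowers the risk of refusal but does not remove it.
- **Logistics.** Bone marrow and fat need different equipment, and early allocation lets the theatre prepare. The documents do not give this as the reason. Group 3 already requires both set-ups in the same operating rooms, so the burden is small.

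**Conclusion.** The point holds as an avoidable risk of unknown size. The chart separates allocation from treatment in an open-label trial with unequal harvest burdens, does not recheck eligibility, and leaves patients randomised but untreated without a rule. Loss in the interval could depend on the arm, and the arm most exposed is the one on which H1 turns. The power cost is small: 0.958 as planned, 0.946 after three evenly spread losses, and 0.915 if four are lost from Group 3 alone. Arm-dependent selection matters more, and the documents do not allow it to be estimated.

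The conclusion assumes that the chart's two separate visits are intended, that untreated patients would have no post-baseline scores, and that the mixed ANOVA is run on complete cases. It does not assert that such losses will occur, or that changing the timing would remove them altogether, since a patient told on the day can still refuse. The change is worth making because it is cheap.

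**What to change.** 1. Reconcile the interval between randomisation and procedure across section 4.a.vii, the flow chart and the Statistical Analysis section.
2. Move the Randomization mark from Visit 4 to Visit 5. Open the allocation after eligibility is reconfirmed and immediately before harvest, or as close to the procedure as theatre logistics allow. Visit 4 then has no marked content and could be dropped.
3. State that every patient whose allocation is opened is followed at all scheduled visits, dated from randomisation if untreated, and analysed in the assigned arm. Report the number randomised but untreated, with reasons, by arm.

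Items 2 and 3 are both needed. Analysis as assigned preserves the comparison, but each untreated patient dilutes the contrast between arms, and late allocation keeps their number low. If same-day allocation proves impractical, shorten the interval and keep item 3.

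The cost is one chart mark and a short protocol paragraph, with possibly one visit fewer per patient. The downside is that both harvest set-ups must be available on the day for every patient.

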- v. Application of the WOMAC Questionnaire (Western Ontario and McMaster Universities Osteoarthritis Index)²³. The Index contains 24 questions five items for pain (score range 0–20), two for stiffness (score range 0–8), and 17 for functional limitation (score range 0–68). Individual question responses are assigned a score of between 0 (extreme) and 4 (None). Individual question scores are then summed to form a raw score ranging from 0 (worst) to 96 (best). Finally, raw scores are normalized by multiplying each score by 100/96. This produces a reported WOMAC Score of between 0 (worst) to 100 (best).
- vi. Pain measurement with the Visual Analogue Scale (VAS). Visual analogue scales (VAS) are psychometric measuring instruments designed to document the characteristics of disease-related symptom severity in individual patients and use this to achieve a rapid (statistically measurable and reproducible) classification of symptom severity and disease control.
 - a) Restriction of pain medication. Any NSAID 15 days before procedure; and 12 months after.
- vii. Extracellular Matrix (ECM) preparation 3 weeks prior to procedure. Infiltration with procaine 2% by repolarization of the cell membrane in order to improve ECM at the areas to work.

* Each patient from all groups will receive 2 injections of procaine before the procedure. On week 1 and 3.
- ix. No cortisone injections will be permitted before or even 3 months previous to the procedure.

b. Intra-operative:

- i. Independent of MSC source and in order to know the amount and types of injected MSCs, flow cytometry will be used processing of the cells immediately after extraction and prior to the injection into

the knee. In 2006, the International Society for Cellular Therapy proposed minimal phenotypic criteria for the definition of cultured MSCs: expression of CD73, CD90, and CD105, and lack of CD11b or CD14, CD19 or CD79, CD45, and HLA-DR expression²⁴. It should be noted that the main criteria for MSCs are (1) plastic adhesion; (2) the above described phenotype; and (3) their tri-lineage differentiation potential²⁴.

- ii. *CD90 FITC, CD73 PE, CD105 PerCP-Cy5.5* phenotypic expression are measured regarding quantity and viability for all groups of patients.
- iii. *CD34PE, CD11b PE, CD19 PE, CD45 PE, HLADR PE, lack of phenotypic expression, will be measured.*

c. Post-operative:

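### After the procedure visit, the flow chart's next adverse event check is Month 3, so early, transient complications are likely to be undercounted or to rest on late recall

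*Combined protocol and SAP*

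**What the plan says.** Main goal (b) opens with "To assess the efficacy and safety of treatment", so safety is a stated aim alongside efficacy. The Statistical Analysis section names the events of interest: "The complications considered in this investigation are pain and hematomas in the surgical place where stem cells were extracted, knee pain, and synovial effusion". It plans to model them, saying that "there will be mixed lineal models generalized for determining the probability of each intervention", but gives no time window and no rule for how events are ascertained.

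The only adverse event schedule is the study flow chart in section 7. Its row "Adverse Event Evaluation" is marked at Visit 5 (Week 6) and at Months 3, 6, 9 and 12. Visits 1 to 4 have no mark. The Visit 5 column also carries the procedures, "Post Op Evaluations" and "Sticks removed" (read here as stitches, which is an assumption).

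Section 4.c, section 7 and the Statistical Analysis section all require VAS and WOMAC at 1 month. The chart has no Month 1 column.

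On the preparation phase, section 4.a says "Each patient from all groups will receive 2 injections of procaine before the procedure. On week 1 and 3". The chart places preparation at Visits 1 and 3, Informed Consent at Visit 2 and randomization at Visit 4.

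**The concern.** The named complications are local consequences of harvest and injection, and the procedure is ambulatory. Events of this kind can begin after the patient has gone home and settle before the next scheduled check. Group 3 needs both cell sources, so its patients undergo two harvests against one in each other group. If the arms differ in complications, the early period is a natural place for the difference to appear, and it is the period the chart covers least.

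The documents give no diary, telephone contact, recall period or rule for reporting between visits. An event missed early can be recovered only from memory at Month 3, reported by a patient who knows the allocation. Early events that were never recorded cannot be reconstructed after the trial.

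**Working it through.** **The plan's own figure.** The plan gives no number for safety. Its one sample-size figure reproduces: λ = f² × N × m / (1 − ρ) = 0.0625 × 54 × 3 / 0.5 = 20.25, with 4 and 102 degrees of freedom and power 0.958. It concerns the efficacy interaction and does not bear on this point.

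**Length of the gap.** Inputs are the visit labels in the flow chart.
- Chart's clock, Month 3 counted from Week 1: 3 × 30.44 = 91 days. Visit 5 falls at day 35 to 42, so the gap is 91 − 42 = 49 days to 91 − 35 = 56 days, or 7 to 8 weeks.
- Months counted from the procedure, as the Statistical Analysis section states: 91 days, or 13 weeks.

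**Where the 1-month visit falls.** Counted from the procedure, it comes 30 days (about 4 weeks) after Week 6, near Week 10. That lies inside the gap, between Visits 5 and 6.

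**Events still present at a later check.** The documents give no durations, so mean durations are assumed here, with exponential resolution: share present = exp(−gap / mean duration).

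| Assumed mean duration | Day 30 (1-month visit) | Day 49 | Day 56 | Day 91 |
|---|---|---|---|---|
| 7 days | 1% | 0.1% | <0.1% | <0.1% |
| 14 days | 12% | 3% | 2% | 0.2% |
| 28 days | 34% | 17% | 14% | 4% |
| 60 days | 61% | 44% | 39% | 22% |

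In every row, most events have resolved by Month 3. The day-30 column shows that a 1-month check limited to events present that day would also miss most short-lived ones. Asking about the whole interval therefore matters as much as adding the visit.

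**What the table does not measure.** If a share c of events is recorded at Visit 5, and this is unrelated to duration, the share neither recorded there nor present at Month 3 is (1 − c) × (1 − share present). The plan does not fix the day of the Visit 5 check, so c is unknown. The complement of each table entry is a ceiling on the loss, reached only if c = 0 and nothing is recalled.

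**What the 1-month scores cover.** VAS and WOMAC measure knee pain, stiffness and function. Haematoma, effusion and harvest-site pain are not recorded as events. Because every patient enters with a VAS of at least 4, a knee pain score does not by itself identify a new complication.

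**Procaine.** 2 × 54 = 108 planned injections, with an adverse event mark at neither of the two preparation visits.

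**The case against.** The strongest reply is that Visit 5 is not simply the injection day. If the row means stitches, their removal must come later, so the column spans a further contact at which adverse events may be checked. This stands: a reader might infer that nobody looks between the injection day and Month 3, and the chart does not establish that. What it shows is that the day of the check is undefined.

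Nor does the plan restrict a check to events present that day. A complication recalled at Month 3 has been seen, though less reliably. A reader might take the complements of the table (56% to more than 99% no longer present) as the share missed. That is not supported: the durations are assumed, and the figures give no credit for events recorded at Visit 5 or recalled later.

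Knee pain is partly captured by the 1-month scores. This stands for that one complication, as a score and not as an event.

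A reader might also infer that the trial would find no difference in complications by design. The documents give no complication rates and no expected excess in Group 3. With 18 per arm, zero observed events leaves a one-sided 95% upper bound of 1 − 0.05^(1/18) = 15.3%, so the comparison is imprecise even with complete recording.

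Finally, procaine is given to all groups before randomization. Missing its events leaves a descriptive gap but cannot bias the comparison of arms.

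The study design figure was not available for this check. If it shows further adverse event contacts, it should be reconciled with the flow chart.

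**Conclusion.** The point holds as a weakness in early safety ascertainment that is cheap to repair. After a Visit 5 check of unspecified day, the schedule leaves about 7 to 13 weeks before the next one, and the text's 1-month evaluation fills that gap only for VAS and WOMAC. Transient complications of the kinds the plan names are likely to be undercounted or to depend on late, unblinded recall, and this weakens the comparison of arms under goal (b).

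The direction rests on the events being short relative to the gap, an assumption the documents neither state nor contradict. The size cannot be fixed from the documents.

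A reader might conclude that the safety objective cannot be answered at all. That goes too far: events found at Visit 5, events that persist or start later, and events that are recalled or reported spontaneously can still be compared. The procaine gap is secondary and descriptive only.

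**What to change.** In the flow chart and case report form:

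1. Give the post-procedure contact (the "Sticks removed" row) its own column, apart from the procedure, and mark an adverse event check there.
2. Add the 1-month visit that the text already requires, mark an adverse event check at it, and state whether the chart's months run from Week 1 or from the procedure.
3. At every check, ask about all events since the last contact, and record onset date, resolution date and site (iliac crest, fat harvest, knee).
4. Report by arm the complications occurring up to the 1-month visit.
5. As a secondary, descriptive item, add an adverse event check for the procaine period, placed after consent. The chart's first preparation at Visit 1 and Informed Consent at Visit 2 must be reconciled.

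The cost is a few more form entries, mostly at contacts that already have to take place. Recorded complication counts will be higher, because more of what happens will be written down.
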